## **OUTCOME MEASURES:**

Due to MOBILITY being a pragmatic and largely observational study, any participant who is deemed eligible by the above criteria will be enrolled in MOBILITY. These criteria, along with providing appropriate informed consent/assent, are the necessary criteria for participation in MOBILITY. We will continue to collect data in a naturalistic manner from all patients who have met these criteria regardless of whether they begin the intervention to which they have been randomized or have not attended all of their clinical follow up appointments. Patients will have follow-up study visits and data collected concurrent with their existing CLINICAL visit schedule.

### **Primary Outcome Measure: BMI z-score**

Raw BMI is calculated as (weight (kg)/ height (m)). Normalized BMI (z-score, adjusted for age and sex), will be calculated using the program provided by the USDA/ARS Children's Nutrition Research Center at Baylor College of Medicine (<http://www.bcm.edu/cnrc/bodycomp/bmiz2.html>). At each site weight will be measured with a Seca scale, model 813, calibrated to the nearest 0.2 kg per manufacturer instructions annually using standard weights. A standard operating procedure on weight and height measurement will be made available to each site, and staff will be trained in its application. Scales will be zeroed before each individual measurement and the patient will be instructed to remove their outer clothing, shoes, backpack, coat, and any other extra heavy clothing. Weight will be recorded to the nearest 0.1 kg. Height will be measured with a wall-secured stadiometer. The stadiometer is not required to be calibrated as stated by manufacturer instructions. Height will be measured without shoes while standing on a flat surface with chin parallel to the floor. The patient's height will be recorded to the nearest 0.1 cm.

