#### **A. SPECIFIC AIMS**

The specific aim of this study is to address the significant gap in the evidence base for metformin (MET) use in overweight and obese youth with Bipolar Spectrum Disorders (BSD).

The overall objective of this prospective, large, PRAGMATIC randomized trial is to study the impact of MET and healthy lifestyle intervention (LIFE) vs. LIFE alone on patient-centered outcomes of body weight, Second Generation Antipsychotics (SGA) adherence and satisfaction, psychiatric symptom burden (e.g. mood/anxiety), and quality of life (QoL). We will also examine metabolic outcomes.

**Specific Aim 1:** Assess the overall and subgroup-specific impact of MET+LIFE versus LIFE alone on short- (6mo) and long-term (24mo) **weight and metabolic health** in overweight and obese youth with BSD.

**H1.1:** Overall, assignment to treatment with MET will abrogate more weight gain and lead to fewer adverse metabolic outcomes than LIFE alone at 6 and 24 months.

**H1.2:** (Heterogeneity of Treatment Effects [HTE]): MET's effectiveness at abrogating weight gain and components of metabolic syndrome will vary with respect to the following factors (see Patient Population and Background for rationale and prior data): 1) Change in BMI z-score from SGA initiation to baseline (in patients already receiving SGA treatment); 2) Prior exposure to and duration of SGA treatment; 3) Baseline BMI z- score; 4) Baseline psychotropic weight burden (in SGA non-naïve patients; as defined in Measures below); 5) BSD as diagnosed by a structured interview; 6) Age; 7) Type of insurance (public/private); 8) Ethnicity (Hispanic/Non); 9) Baseline insulin resistance (HOMA-IR); 10) Race (African-American (AA) vs non-AA).

**Specific Aim 2:** Assess the overall and subgroup-specific impact of MET+LIFE vs. LIFE alone on short- (6mo) and long-term (24mo) **SGA adherence and treatment satisfaction**, including assessment of how these effects may be mediated by MET effects on weight gain.

**H2.1:** Overall, assignment to treatment with MET will lead to better SGA adherence and greater treatment satisfaction than LIFE alone after both 6 and 24 months.

**H2.2:** (HTE): MET effectiveness with regard to SGA adherence will vary with respect to: 1) Baseline weight acceptability; 2) Baseline psychotropic medication treatment acceptability; 3) Type of insurance (public/private).

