Furthermore, the effects on weight and other metabolic parameters are small compared with pharmacological interventions. Despite these limitations, The American Medical Association (AMA) 2007 provides guidelines on interventions for youth ages 2-19 years old who meet CDC criteria for “at risk for overweight” and “overweight” (BMI%  $\geq$ 85%ile) that involve simple education regarding diet and physical activity, i.e., healthy lifestyle intervention. Although these guidelines were not specifically developed for mentally ill youth, the approach has advantages for this population, including simple dietary guidelines and inexpensive strategies to reduce sedentary behavior. This approach is similar to the standardized Healthy Eating Plan and Physical Activity education (LIFE) that will be provided to each participant of the proposed trial.

**Metformin (MET) for Obesity in Youth.** Pharmacological therapies, such as MET, supplement the effects of lifestyle interventions for weight loss. MET targets a molecular mechanism for weight gain, i.e., hypothalamic neuronal AMP kinase, a metabolic “fuel sensor”. SGAs directly affect hypothalamic AMP kinase through histamine H1 receptors, decreasing leptin and insulin sensitivity. MET is an oral anti-hyperglycemic, insulin- sensitizing agent that reduces hepatic gluconeogenesis and is noteworthy among diabetes treatments for not promoting weight gain. MET is approved by the USFDA for treatment of type II diabetes in youth >10 years. MET decreases food intake in obese, non-diabetic individuals. A recent meta-analysis of 14 randomized clinical trials (N>1000) examining the effectiveness of MET for obesity in youth found an average BMI reduction of -1.38 (95% CI, -1.93 to -0.82) over 6 months compared with controls. Although a greater effect was seen for youth with a BMI > 35 at baseline, the authors concluded that a large trial is needed to determine the benefits to subgroups. Smaller meta-analyses report BMI reductions of -1.1 to -2.7 in obese youth compared with placebo or lifestyle intervention alone, in trials ranging from 6-12 months with MET dosages of 1000-2000mg/day. Fasting insulin resistance, glucose homeostasis, and dyslipidemia improved after MET. In these studies of youth from 8-18 years old, MET was well-tolerated at up to 2000mg/day.

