### C. PRELIMINARY STUDIES

**Pilot naturalistic study:** 47 youth with a BMI > 85%ile and prescribed an SGA were treated with MET at CCHMC's residential treatment facility, using a MET dose titrated to 850 mg 2x/day over 2-4 weeks, with a further increase to 1000 mg 2x/day by 2 months if weight gain continued. BMI z score was the primary outcome measure. Electronic medical record data from two groups of these MET-treated patients were analyzed (MS submitted for publication): Group 1 (SGA non-naïve) was taking SGAs for at least 2 months (mean  $\pm$  SD = 9.2  $\pm$  7.2 months, range= 2.3 - 24.9) prior to MET initiation (n=29, 47% girls, age=13.9 years  $\pm$  2.5); Group 2 (SGA naïve) started on MET and SGAs simultaneously (n=18; 59% girls, age=14.2 years  $\pm$  2.8). The groups were similar, and, as in our previous report, 40% received > 1 psychotropic medications. 80% of the SGA non-naïve patients had weight gain > 7% over the 2 months prior to MET initiation and exhibited a 0.45 sd increase in their BMI z score (Figure 1). Surprisingly, more of the SGA naïve (94%) than the SGA non-naïve (78%) patients had a BMI > 95%ile at MET initiation. BMI Z score was stabilized by MET in both groups, but there was a significant group by month interaction ( $p=0.003$ , generalized linear model), even after controlling for the higher baseline BMI z score ( $p=0.002$ ).

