The basic model for outcomes will be a GLMM with change from baseline to either 6- or 24- months as the dependent variable. Independent variables will include fixed-effect terms for randomized treatment group (MET), baseline value of the outcome, and random site effects. For HTE analyses, a baseline value-by-MET interaction (to assess HTE due to baseline status) will be included, and for particular domains additional continuous or categorical covariates and treatment-by-covariate interaction terms will be added to assess HTE. Outcomes within each domain will share the same set of HTE terms, specified in the Specific Aims. Because the subgroups are in general correlated (e.g., duration of SGA treatment, weight gain history and psychotropic weight burden will be correlated with baseline BMI), we will include multiple first-order HTE terms simultaneously (to assess heterogeneity independently attributable to each moderator), but will also fit separate models for each term to gauge the impact of this correlation on our conclusions. Higher-order treatment-by-covariate interactions will not be included a priori, but will be explored with rigorous adjustment for multiple testing, using step-down testing (removing highest-order interaction terms first) or information criteria based on penalized likelihoods to guide model selection.

**Marginal Structural Modeling for Causal Inference:** SA1 concerns the overall and sub-group specific effects of MET on abrogation of weight gain (with changes in BMI z-score from baseline as outcomes) and metabolic health, particularly metabolic syndrome and its component criteria. BMI and adherence measures are obtained at all study visits, so our models for these measures will use all available observations by treating the longitudinal series of changes in these variables and SGA treatment as dynamically dependent on each other. We will use marginal structural models to address this bi-directional dependence, computing the probability of SGA treatment regimen change at each visit within weight gain treatment regimen groups and using appropriately normalized versions of the inverse of the probability as the stabilized weights.

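### Weight effects and their modification by baseline BMI are specified only in BMI z-score units, so under a right-skewed growth reference moderator 3 can be significant because of the scale alone

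*Combined protocol and SAP*

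**What the plan says.** The outcome section is headed "Primary Outcome Measure: BMI z-score" and states that "Normalized BMI (z-score, adjusted for age and sex), will be calculated using the program provided by the USDA/ARS" Children's Nutrition Research Center. Raw BMI is defined in the same paragraph, but no analysis of it is named. The documents give no formula or constants for the z-score.

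In Data Analysis and Data Monitoring, the marginal structural modelling paragraph describes Aim 1 weight analyses "with changes in BMI z-score from baseline as outcomes". Specific Aim 1, H1.2, lists as a moderator "3) Baseline BMI z- score". The basic model has change to month 6 or month 24 as dependent variable, and for heterogeneity analyses "a baseline value-by-MET interaction (to assess HTE due to baseline status) will be included".

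Aim 1 also has outcomes that are not in z units: metabolic syndrome and its individual criteria (Secondary Outcome Measures), which share the same moderators.

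On prior evidence, the Background cites a meta-analysis of metformin in obese youth with a mean BMI reduction of 1.38 over 6 months, and adds that "a greater effect was seen for youth with a BMI > 35 at baseline". In the pilot (Preliminary Studies), "more of the SGA naïve (94%) than the SGA non-naïve (78%) patients had a BMI > 95%ile at MET initiation".

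**The concern.** A z-score from a right-skewed reference compresses the upper tail: each further BMI unit adds less z. Entry starts at the 85th percentile with no upper limit, so the trial can enrol far into that tail. Outcome and moderator 3 are both on the compressed scale. A metformin effect that is identical in BMI units for every patient then gives a smaller z effect at higher baseline z, and the interaction test picks this up as heterogeneity.

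Moderator 3 is meant to help show who benefits from metformin. The scale effect runs towards less apparent benefit in the heaviest patients, whereas the Background reports more benefit in them in BMI units. Analysed on z alone, a real gradient could be hidden or appear reversed, and the plan has no second weight scale that would reveal this.

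**Working it through.** The plan states no figure on this point, so there is none to reproduce. The check asks what a right-skewed reference would do to the planned analysis.

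**1. Conversion of a fixed BMI loss to z**

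Inputs: loss of 1.38 BMI units (Background). Assumed, not in the documents: LMS form, median M = 19, S = 0.13, L from 1 (no skew) to -2.5, and example BMIs of 24, 30 and 36 at the same age and sex.

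Formula: z = ((BMI/M)^L - 1)/(L·S), or ln(BMI/M)/S when L = 0.

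Example, L = -2, so z = (1 - (BMI/19)^-2)/0.26:
- BMI 24: (1 - 0.6267)/0.26 = 1.436. BMI 22.62: (1 - 0.7055)/0.26 = 1.133. Loss = 0.303 z.
- BMI 36: (1 - 0.2785)/0.26 = 2.775. BMI 34.62: (1 - 0.3012)/0.26 = 2.688. Loss = 0.087 z.
- Ratio of the unrounded losses: 3.48.

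| L | z loss from BMI 24 | from BMI 30 | from BMI 36 | ratio 24 to 36 |
|---|---|---|---|---|
| 1 (no skew) | 0.559 | 0.559 | 0.559 | 1.0 |
| 0 (log) | 0.456 | 0.362 | 0.301 | 1.5 |
| -1 | 0.372 | 0.235 | 0.162 | 2.3 |
| -1.5 | 0.336 | 0.189 | 0.119 | 2.83 |
| -2 | 0.303 | 0.152 | 0.087 | 3.48 |
| -2.5 | 0.274 | 0.123 | 0.064 | 4.28 |

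M and S cancel from the ratio, so at a given age and sex it depends only on L and on the two BMIs compared. A uniform 5% loss, in place of a fixed number of units, still shrinks between BMI 24 and BMI 36: 1.5-fold at L = -1 and 1.8- to 2.8-fold for L from -1.5 to -2.5.

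**2. Consequence for the interaction test**

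Simulation of the baseline-by-metformin interaction: 1800 patients, 1:1 (from the plan). Assumed: M = 19, S = 0.13; baseline BMI = 85th percentile plus a gamma variable (shape 1.6, scale 5), capped at 55; control drift +0.5; no site effects; robust standard errors; two-sided 0.05; 400 runs. The z analysis uses baseline z as moderator, and the raw analysis uses baseline BMI.

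| True effect in BMI units (SD of change) | z scale, interaction significant, L = -1 / -2 / -3 | raw BMI, interaction significant |
|---|---|---|
| none (2) | 3.5% / 5.5% / 6.2% | 4.0% / 6.2% / 5.2% |
| constant 0.7 (2) | 63% / 82% / 86% | 5.0% / 5.0% / 5.5% |
| constant 1.38 (2) | 99.8% / 100% / 100% | 4.0% / 6.8% / 5.2% |
| constant 1.38 (3) | 90% / 94% / 96% | 6.5% / 6.0% / 4.8% |
| proportional to BMI, mean 1.38 (2) | 64% / 94% / 98% | 88% / 86% / 85% |

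The z-scale interaction coefficient is positive, meaning less apparent benefit at higher baseline z: +0.10 to +0.25 for the constant effect of 1.38 and +0.05 to +0.15 for the proportional effect. In the last row the BMI effect is truly larger in heavier patients, yet the z scale shows the opposite sign. In the first row all tests stay close to 5%.

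**3. No scale is neutral**

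Percentage of the 95th percentile is BMI divided by an age- and sex-specific constant. On it, a uniform 5% loss is 0.05 × 24 = 1.2 units at BMI 24 and 0.05 × 36 = 1.8 units at BMI 36, a 1.5-fold gradient the other way. On percent change, a constant 1.38 units is 1.38/24 = 5.8% at BMI 24 and 1.38/36 = 3.8% at BMI 36.

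**The case against.** The best case for the plan has five parts.

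- **The size is not in the documents.** The plan names a program, not its constants, and the compression depends on L and on which BMIs are compared. This stands: several-fold compression is conditional on the assumed skew. The direction, for any right-skewed reference, is not.
- **Interactions always depend on scale.** This stands, as step 3 shows. It argues against letting one alternative scale decide the claim. It does not justify reporting only one scale.
- **The pilot points the other way.** Preliminary Studies lists higher baseline BMI z-score as a determinant of metformin response, in a study whose outcome was BMI z-score. That is fair evidence against saying the plan will reach a reversed conclusion. The pilot was an uncontrolled series of 47, so it does not exclude compression.
- **The main comparison is unaffected.** A reader might infer that the primary test is biased. It is not: randomisation protects H1.1, and with no metformin effect the simulated interaction test also kept its size. Power for the overall effect falls only modestly. In one simulation (L = -2, SD of change 2.5, constant effects of 0.3 and 0.4 units) it was 66% and 86% on z, against 74% and 92% on raw BMI.
- **The z-score has a purpose, and other outcomes exist.** It adjusts for age and sex in growing children, and the metabolic outcomes are outside z units. Both points hold. The metabolic criteria do not, however, show how the amount of BMI change varies with baseline BMI.

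A reader might also take the prior randomised study in Preliminary Studies as proof of compression, by dividing its z difference by its weight difference. The documents do not support this: the z changes are at 12 and 24 weeks, while the weights are labelled 24 months. Nor can the pilot's 78% and 94% above the 95th percentile be carried over to the trial. They come from 29 and 18 youths at one residential facility, and being above the 95th percentile does not mean a BMI near 36.

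**Conclusion.** The point holds for weight, and for moderator 3 in particular. Treatment effect and effect modification by baseline BMI are defined only on BMI z-score. If the reference is right-skewed, a fixed BMI loss counts about 2.3 to 4.3 times less at BMI 36 than at BMI 24 (L from -1 to -2.5), about 1.5 times less for a logarithmic reference, and equally without skew. Under the simulated conditions a constant effect of 1.38 units made the interaction significant in 90% to 100% of runs. Those percentages rest on the assumed BMI distribution, SD and L. The direction, less apparent benefit in heavier patients, follows from the skew.

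The documents do not support the stronger readings that H1.1 is invalid, that all Aim 1 outcomes share the problem, or that the trial will necessarily report the wrong direction. What is at risk is the interpretation of one pre-specified moderator and of the effect size in the heaviest patients.

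**What to change.** Keep BMI z-score as the primary outcome and add to the analysis plan:

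1. Supportive analyses of weight change at months 6 and 24 on two further scales, both adjusted for age and sex: BMI as a percentage of the age- and sex-specific 95th percentile, and percent (log) change in BMI.
2. Moderator 3 and the baseline-by-metformin interaction on the same two scales, with the interaction estimate and confidence interval reported on all three.
3. An interpretation rule: effect modification by baseline BMI is described as scale-dependent unless its direction agrees across the scales. No single alternative scale decides the claim.

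Under this rule, neither a constant nor a purely proportional BMI effect should be read as heterogeneity, because each gives no gradient on one of the added scales.

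The cost is protocol wording, a recalculation from height, weight, date of birth and sex that are already recorded, and additional outcome scales to report. Visits, sample size and the primary analysis do not change.

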### **Secondary Outcome Measures:**

**Metabolic Health and Nutrition:** As per clinical standards, blood pressure will be measured after 5 minutes of sitting at each patient visit. A minimum of 8-hour fasting total cholesterol, low-density lipoprotein (LDL)-cholesterol, high density lipoprotein (HDL)-cholesterol, triglycerides, glucose, insulin, and glycosylated hemoglobin (HbA1c) will be recommended for collection (see Table 2). For HTE analyses the homeostatic model assessment for insulin-resistance (HOMA-IR) will be computed as:

(Insulin [IU/mL] x Glucose [mg/dL] /405). Following the modified ATPIII guidelines, metabolic syndrome is defined when  $\geq 3$  of the following: 1) abdominal obesity (BMI  $>90\text{th}$  percentile, as in NHANES study of metabolic syndrome in youth; 2) blood pressure  $\geq 90\text{th}$  percentile for height, age, sex; 3) fasting triglycerides  $\geq 150$  mg/dL; 4) low HDL cholesterol (males  $<40$  mg/dL and for females  $<50$  mg/dL); 5) fasting glucose  $\geq 100$  mg/dL Fulfillment of individual criteria and metabolic syndrome will be outcome measures.

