## **E. EXPERIMENTAL DESIGN & METHODS**

### **a. Methods and Procedures**

**Study Overview:** We propose a prospective, large, PRAGMATIC, randomized trial to study the impact of MET and healthy lifestyle intervention (LIFE) vs. LIFE alone on patient-centered outcomes of body weight, SGA-adherence and satisfaction, psychiatric symptom burden (e.g. mood/anxiety), and QoL. We will also examine metabolic outcomes.

The focus of the pragmatic trial is to determine which intervention is most effective through observation of care as usual conditions or in “real-world clinical settings” rather than under controlled experimental circumstances. Information should be collected when available as part of routine clinical practice rather than through study-specific procedures, with minimal interference to clinical practice. Adherence to protocol recommendations from practitioners and patients are observed and documented throughout the study.

**Subjects:** We propose to recruit approximately 1800 overweight/obese youth with BSD who are prescribed SGAs from at least 40 public and private mental health practices (approximately 900 each from sites under the coordination of University of Cincinnati, Midwestern center and from within the sites under the Northwell Health East Coast coordinating center), to participate in the proposed patient-centered large pragmatic trial examining the effectiveness of MET and LIFE vs. LIFE alone. Patients will be eligible for study participation if they are:

1. Inpatient or outpatient age 8-19 years inclusive; participants must live with a parent, guardian, or caregiver;
2. Fluent in English;
3. Diagnosed or told by a clinician that they have any of the following bipolar spectrum disorders (BSD): bipolar I, bipolar II, unspecified bipolar and related disorders, Disruptive Mood Dysregulation Disorder (DMDD), cyclothymic disorder, other specified bipolar and related disorders, as well as mood disorder not otherwise specified (if diagnosed in the past as per DSM-IV);
4. Body mass index  $\geq 85\text{th}$  percentile for age and sex by standard growth charts;
5. Received a new or ongoing prescription for at least one SGA (i.e., olanzapine, clozapine, risperidone, quetiapine, aripiprazole, ziprasidone, iloperidone, lurasidone, paliperidone, brexpiprazole or cariprazine) that is not prescribed as a PRN medication

Additionally, patients will be excluded by the following:

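### The named metabolic outcomes are yes/no criteria only; BMI above the 90th percentile sits just above the entry threshold and adds little, and the blood pressure and laboratory values should be named as baseline-adjusted continuous outcomes.

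*Combined protocol and SAP*

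**What the plan says.** The Metabolic Health and Nutrition paragraph under Secondary Outcome Measures (Section E.a) lists blood pressure, total, LDL and HDL cholesterol, triglycerides, glucose, insulin and HbA1c as measured or recommended for collection. It then defines metabolic syndrome as at least three of five cut-offs: BMI above the 90th percentile, blood pressure at or above the 90th percentile for height, age and sex, triglycerides, HDL and fasting glucose. The outcomes themselves are given in one sentence: "Fulfillment of individual criteria and metabolic syndrome will be outcome measures". HOMA-IR is defined for the heterogeneity analyses.

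The analysis section (E.b, Marginal Structural Modeling) describes the Aim 1 outcomes in the same terms: "metabolic health, particularly metabolic syndrome and its component criteria". Weight is the exception, because it is analysed on its own scale, "with changes in BMI z-score from baseline as outcomes", and BMI z-score is the primary outcome.

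The model is stated once for all outcomes (E.b, Analyses of Specific Aims): "The basic model for outcomes will be a GLMM with change from baseline to either 6- or 24- months as the dependent variable". It includes the baseline value as a covariate, and the section says that generalised linear mixed models allow for a range of distributions. It does not say what form the model takes for a yes/no criterion.

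Entry requires BMI at or above the 85th "percentile for age and sex by standard growth charts". In the sponsor's pilot (Section C), "more of the SGA naïve (94%) than the SGA non-naïve (78%) patients had a BMI > 95%ile at MET initiation". Laboratory tests other than the pregnancy test are suggested and not required (Laboratory Measures; Table 2).

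**The concern.** Hypothesis H1.1 predicts fewer adverse metabolic outcomes with metformin, and the named outcomes are a blunt way to test it.

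- **Criterion 1 starts near its ceiling.** Only patients from the 85th to the 90th percentile can be free of it at baseline. For everyone else it counts towards metabolic syndrome from the first visit, so the three-of-five rule becomes two of the remaining four.
- **Single cut-offs lose information.** The other four criteria reduce numeric values to yes or no. Because laboratory tests are optional, three of those four will have fewer observations to begin with.
- **Some relevant values appear in no criterion.** Insulin, HbA1c and LDL are in none of the five, although the Background describes metformin as insulin-sensitising and cites improved fasting insulin resistance.

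At stake is the reading of a null metabolic result. It could reflect the definitions and not the treatment, and a favourable continuous result would look like a post hoc choice because no such outcome had been named.

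**Working it through.** The available text gives no power, effect size or event rate for the metabolic outcomes, so there is no sponsor figure to reproduce.

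**1. Share meeting criterion 1 at baseline**
- If BMI followed the growth-chart reference above the entry threshold: 0.10 / 0.15 = 67%.
- From the pilot (94% of 18 and 78% of 29 above the 95th percentile): (0.94 × 18 + 0.78 × 29) / 47 = (16.92 + 22.62) / 47 = 84%. This counts patients above the 95th percentile, so the share above the 90th is at least that.

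**2. Distance to the threshold**
- Standard normal values are 1.036 (85th), 1.282 (90th) and 1.645 (95th). A patient at the 95th must fall 1.645 − 1.282 = 0.363 z to lose the criterion.
- The IMPACT results in Section C give 24-week changes of −0.088 (metformin) and +0.040 (control), a difference of 0.128. The distance is 0.363 / 0.128 = 2.8 times that difference.
- Individual changes vary, so some patients do cross. Taking 0.5 as the SD of change (one reading of the pilot's 0.27+0.5), the crossing probability from the 95th percentile is Φ((−0.363 + 0.088)/0.5) = 29% with metformin and Φ((−0.363 − 0.040)/0.5) = 21% in control. With an assumed SD of 0.3 it is 18% and 9%. Patients further above the 95th cross less often.

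**3. Whole-sample illustration**

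Baseline z is normal, truncated at the 85th percentile. The pilot-like settings use mean 2.0 with SD 0.42 and mean 2.1 with SD 0.5, which put 81% and 83% above the 95th percentile and about 97% above the 90th. The mean changes are those above, and the SD of change runs from 0.2 to 0.5.

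| Baseline setting | Lose criterion 1, metformin | Lose criterion 1, control |
|---|---|---|
| Pilot-like | 5–14% | 2–10% |
| Growth-chart reference | 19–28% | 9–21% |

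Power at 810 per arm (900 less 10%, from the expected retention of about 90%), assumed two-sided alpha 0.05, pilot-like settings:

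| SD of change | Criterion 1 (yes/no) | BMI z change |
|---|---|---|
| 0.5 | 65–73% | 99.9% |
| 0.3 | 75–83% | 100% |
| 0.2 | 80–86% | 100% |

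At SD 0.5, 90% power needs 1283 to 1552 per arm for criterion 1 and 321 for BMI z. Under the growth-chart reference, criterion 1 reaches about 90% power at SD 0.5. The yes/no comparison uses follow-up status without baseline adjustment, and adjustment would narrow the gap somewhat.

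**4. Information kept by one cut-off**

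For a normal marker with a shift effect, efficiency relative to the continuous value is φ(z_p)² / [p(1 − p)], where p is the prevalence.

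| Assumed p | φ(z_p) | Efficiency |
|---|---|---|
| 5% | 0.103 | 0.22 |
| 10% | 0.175 | 0.34 |
| 20% | 0.280 | 0.49 |
| 30% | 0.348 | 0.58 |
| 50% | 0.399 | 0.64 |

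For example, at 10%: 0.1755² / 0.09 = 0.34. The documents give no prevalence for these cut-offs. The Background gives 12–50% for hyperinsulinemia and dyslipidemia in SGA-treated youth, which are not the same definitions.

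**The case against.** Several points limit how far this goes, and they stand.

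- **Criterion 1 is not fixed.** A reader might infer that it cannot show any effect. The calculation says otherwise: patients who meet it can revert, those between the 85th and 90th percentile can move either way, and illustrative power is moderate and not nil. The pilot share comes from 47 youths in one residential facility, whereas the trial recruits from about 40 community centres. At 67% the criterion is far from constant.
- **No information about weight is lost.** The continuous form of criterion 1 is the primary outcome.
- **Continuous values are not excluded.** They sit under the Secondary Outcome Measures heading, and the analysis section names the criteria as a particular focus without ruling out other analyses. The gap is one of specification.
- **Dichotomising need not discard most of the information.** At 30% prevalence a cut-off keeps 58%. The loss exceeds half only at lower prevalences, and all of these are assumed.
- **The plan does not say that yes/no criteria will be differenced.** A reader might infer an outcome of −1, 0 or 1 from the change-score model. The baseline term and the stated range of distributions largely answer that worry. What remains is that no model for binary outcomes is written down.

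It can also be argued that metabolic syndrome is a recognised youth definition and should not be ranked below a list of markers, and that raw blood pressure would lose the standardisation in the present criterion. Both are fair, and the fix below respects them.

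**Conclusion.** The concern holds as a matter of sensitivity and specification. The plan commits only to yes/no metabolic outcomes. One of them will be met at baseline by about two thirds of patients on the growth-chart reference, and by at least about 84% if the pilot is representative. That criterion repeats the primary outcome with less power, and for those patients it turns metabolic syndrome into two of four. For the remaining markers, one cut-off keeps roughly a third to three fifths of the information at prevalences of 10% to 30%, assuming approximate normality and a shift effect. The power figures are illustrations that rest on an assumed baseline distribution, SD of change and alpha.

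The documents do not support saying that criterion 1 cannot move, that continuous analyses are ruled out, or that a null result is built in. This is worth correcting because the remedy is cheap. Part of the documents was not available for this review, so statements that something is absent apply to the text supplied.

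**What to change.** Amend the Metabolic Health and Nutrition paragraph and the analysis section as follows.

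1. Name as secondary outcomes the 6- and 24-month continuous values of fasting triglycerides, HDL, LDL, glucose, insulin and HbA1c (log scale where skewed), and blood pressure standardised for age, sex and height. Adjust each for its own baseline value.
2. Keep metabolic syndrome and criteria 2 to 5 as outcomes. Analyse each as status at follow-up, adjusted for baseline status, in a logistic mixed model with the planned site effects, and not as a change score.
3. Do not count criterion 1 as a separate efficacy outcome. Report reversal among those who meet it at baseline, and new onset among the rest, descriptively by arm.

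No new data collection is needed, although the laboratory outcomes can use only the tests done in routine care. The cost is a few more secondary models, which should be reported as secondary without a confirmatory claim.
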